4.6.3 Goal Attainment Health Outcomes (Aim 2)

Unconditional means models were run for each outcome and the intraclass correlation was calculated to assess for dyad dependence. A three-level mixed model (participants nested within dyads over time) was used to assess changes in weight, BMI,

systolic blood pressure, fruit and vegetable intake, and physical activity. Both unadjusted and adjusted models were run. Church site, dyad relationship (i.e., friend, family or acquaintance), dyad assignment (whether dyads chose or were assigned their partner), and participant characteristics (age, sex, education) were added as model covariates. Dependence of participants during the second nine weeks was accounted for by creating a dichotomous variable to separate measurements taken before participants were paired and measurements taken after they were paired.

First, significant changes from baseline to 18 weeks were assessed. Second, significant changes during the first nine weeks before participants were paired, compared to the second nine weeks after they were paired, were assessed. Third, three interaction terms were entered into three different models to assess whether or not dyad relationship type, dyad partner assignment, or dyad communication frequency influenced changes in health outcomes while participants were paired. Additional descriptive statistics were generated to assess the proportion of participants who were able to achieve clinically significant weight loss (weight loss $\geq 5\%$ of body weight) (Leahey, Kumar, Weinberg, & Wing, 2012; West, Coulon, Monroe, & Wilson, 2016) as well as the recommended servings of fruits and vegetables and daily minutes of physical activity.

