4.4.2 Intervention

4.4.2.1 The Existing Faithful Families Thriving Communities Program

Faithful Families Thriving Communities (FF) is a practice tested healthy weight and lifestyle promotion curriculum developed through a partnership with the North Carolina Department of Health and North Carolina State University (Hardison-Moody & Yao, 2019). The program consists of nine weekly health education classes delivered at the faith community by a North Carolina Cooperative Extension nutrition educator (referred to as “nutrition educators” going forward). Church lay leaders co-lead the program with nutrition educators by adapting elements of the curriculum to the needs of

their community and integrating spiritual elements such as a song or scripture. Classes focus on nutrition and physical activity (e.g. Choosing More Fruits and Vegetables, Making Smart Drink Choices, Choosing To Move More Throughout The Day). Each session involves a Powerpoint[®] lecture, group discussion questions, a physical fitness activity, and cooking demonstrations or tastings. ‘Faithful Families Thriving Communities’ is based on the Socioecological Model of health and therefore encourages faith community changes at the policy, interpersonal, and intrapersonal levels as well (Hardison-Moody & Yao, 2019). Faithful Families Thriving Communities has been implemented in faith communities across the state of North Carolina for the past 12 years (Hardison-Moody et al., 2011) . Program evaluations show communities enjoy the program and want to continue to improve health after it ends. Thus, a peer support component was designed to augment the existing program and allow faith communities to continue to improve their health by building capacity within the organization for members to support one another.

Table 6. 18 Week Dyadic Peer Support Program Outline

Weeks 1-9: Health Education Classes	Weeks 10-18: Dyadic Peer Support		
‘Choosing More Fruits and Vegetables’ ‘Plan Know What’s for Dinner’ ‘Shop for Value, Check the Facts’ ‘Shop: Get the Best for Less’ ‘Fix it Fast, Eat at Home’ ‘Fix it Safe’ ‘Making Smart Drink Choices’ ‘Choosing to Move More’ ‘Making the Connection’	Week 10: Dyad Peer Support Training Session	Week 14: Group Meeting Progress Challenges Strategies	Week 18: Group Meeting End of Program

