4.4.3 Participants and Setting

The inclusion criteria for churches were faith communities with predominantly African American members in one of three counties served by Expanded Food and Nutrition Education Program (EFNEP) nutrition educators. Participant criteria were adults ages 18 years and older who identify as African American; reported being church members or regular church goers; speak, read and write English; willing to complete

study activities and assessments; and able to engage in moderate physical activity. (e.g., walking – based on their own activity level and assessment).

This feasibility study captured qualitative and quantitative data. Data from qualitative interviews generally reaches information saturation between 10-15 interviews (Guest, Bunce, & Johnson, 2006). Thus, a sample size of 20 dyads or 40 participants was planned to ensure data saturation and account for an attrition rate of 30%, as found in a meta-analysis of weight loss programs (Lemstra, Bird, Nwankwo, Rogers, & Moraros, 2016). Also, because statistical significance is not the aim of this feasibility study, a sample size of 40 was considered sufficient to allow insights into patterns of change for quantitative outcomes such as weight and physical activity (Leahey & Wing, 2012; O'Brien et al., 2015). Due to great interest, 80 members across the three sites (site one – 18 members, site two – 24 members, site three – 38 members) were enrolled.

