4.4.4 Procedures

Three county nutrition educators were recruited to participate. Before starting recruitment, the PI, program director and county nutrition educators met to review the program purpose, timeline and how to integrate intervention activities. Each nutrition educator works in one county. After meeting with the PI and reviewing the program, nutrition educators began recruiting churches in their counties via word of mouth, online searches, and face-to-face visits. Faith communities were recruited from May-November of 2018. A search of African-American faith communities and faith community-affiliated organizations was conducted via online searches, neighborhood canvassing, and word of mouth. Faith communities and faith community-affiliated organizations were contacted

via email, their Facebook sites, phone, community organization board meetings, or face-to-face visits.

Initial contact of churches was made by the PI or county nutrition educators. A total of 62 churches were approached. Contact was made with 36 to introduce the program and provide contact information to schedule a follow-up meeting if interested. Of the seven churches that expressed interest, three were ready to begin immediately and selected to start the program. No additional churches were selected because it was anticipated that the first three would be able to recruit the desired sample size of 40 participants. After agreeing to participate, lay leaders, educators, the faith community pastor and the PI helped to recruit church members through church announcements describing the program and flyers.

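### No church-by-time term is described for the Aim 2 models, so the three tests of dyad moderators of change can be confounded by church

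*Combined protocol and SAP*

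**What the plan says.** Section 4.6.3 asks three questions, all about change: from baseline to week 18, in the first nine weeks against the second nine, and whether dyad features influenced change in the paired phase.

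- **Model.** "A three-level mixed model (participants nested within dyads over time) was used to assess changes in weight, BMI" and the other outcomes. Church is not a level. "Both unadjusted and adjusted models were run".
- **Covariates.** "Church site, dyad relationship (i.e., friend, family or acquaintance), dyad assignment (whether dyads chose or were assigned their partner), and participant characteristics"; the sentence ends "and participant characteristics (age, sex, education) were added as model covariates".
- **Interactions.** For the third question, "three interaction terms were entered into three different models to assess whether or not dyad relationship type, dyad partner assignment, or dyad communication frequency" influenced change. Table 7 mentions interactions without listing them. The time coding inside these terms is not given, nor is it said whether the moderator models also carry the covariates. A before/after-pairing indicator is described as the way to handle dependence once partners are matched.

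On the churches:

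- Enrolment was "site one – 18 members, site two – 24 members, site three – 38 members" (4.4.3).
- "Each nutrition educator works in one county" (4.4.4), and 4.5.2 refers to the educator assigned to each church.
- "Church lay leaders co-lead the program with nutrition educators by adapting elements of the curriculum to the needs of" their community (4.4.2.1).
- Lay leaders and the PI matched participants who had no partner preference (4.4.2.2).
- Church is compared at baseline (4.6.1) and tested as a predictor of communication frequency (4.6.2).

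**The concern.** The plan treats church as a possible source of variation at baseline and in communication frequency, but describes no term that lets change differ by church, although change is the Aim 2 target.

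Two things follow. Agreement between the unadjusted and adjusted change could be read as reassurance when, with complete data, it is a property of the model. And a difference in change between, say, chosen and assigned partners could reflect which church the dyads belong to. Such a result might shape how dyads are formed in a later study. With 38 of 80 members at one site, a single pooled change also does not show whether the three churches agree.

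**Working it through.** The plan states no power, effect size or SD that depends on this point, so there is no figure to reproduce. The site sizes 18 + 24 + 38 = 80 and the 30% attrition allowance come from 4.4.3. Every effect size, partner-choice share and SD below is an assumption.

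**1. Main effects and change, complete data.** Write the outcome of person i at visit t as y(i,t) = b0 + τ(t) + γ·x(i) + random effects + error, with x(i) constant over time. Then the expected value of y(i,18) − y(i,1) is τ(18) − τ(1), and γ·x(i) cancels. A generalised least squares check (80 people in 9, 12 and 19 dyads; weeks 1, 9, 14, 18) gave time effects of −1.713785 and −2.107027, with SEs 0.270852 and 0.316066. They were identical to six decimals with and without the covariates.

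**2. Main effects and change, with dropout.** With three visits, about 30% dropout depending on the covariates, and a true week-18 change of 0.40 (SD units):

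| Correlation between a person's visits | Unadjusted | Adjusted |
|---|---|---|
| 0.8 | 0.385 | 0.404 |
| 0.5 | 0.351 | 0.404 |
| 0.3 | 0.318 | 0.397 |

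Here the main effects remove bias, most where the correlation is low, as is plausible for fruit and vegetable intake and physical activity. For a weight-like outcome with very high correlation, the mean absolute shift was below 0.001 kg.

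**3. Moderator with no true effect, closed form.** If church c has paired-phase change δ(c), the expected chosen-minus-assigned difference without church-by-time is Σ δ(c) × [P(c | chosen) − P(c | assigned)]. It is zero if the δ(c) are equal or if the churches have the same share of chosen partners.

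Assume δ = 0, −1, −2 kg and 30, 50, 70% choosing.

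- Chosen: 18 × 0.3 = 5.4, 24 × 0.5 = 12, 38 × 0.7 = 26.6; total 44. Mean change = (−12 − 53.2)/44 = −1.482 kg.
- Assigned: 12.6, 12, 11.4; total 36. Mean change = (−12 − 22.8)/36 = −0.967 kg.
- Spurious difference: −1.482 − (−0.967) = −0.515, or about −0.52 kg.
- Pooled change: (−24 − 76)/80 = −1.25 kg, so the artefact is 0.515/1.25 = 41% of it.

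The same sum gives −0.26 kg at 40/50/60%, −0.78 kg at 20/50/80%, and 0 at 50/50/50%.

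**4. False-positive rate.** Regression on dyad-mean paired-phase change, assumed SD 1.9 kg, two-sided 5% level, 1,500 replicates, δ = 0, −1, −2 kg, no true moderator effect. Forty dyads means all 80 people are paired; 28 = 40 × 0.7.

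| Share choosing partner | Bias, 40 dyads | False positives, 40 dyads | False positives, 28 dyads |
|---|---|---|---|
| 50/50/50% | 0.00 kg | 5.5% | 5.1% |
| 30/50/70% | −0.50 kg | 12.1% | 9.3% |
| 10/50/90% | −1.09 kg | 37.6% | 28.1% |

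With no church gap in change, the 40-dyad rate stayed at 4.5–5.5% whatever the shares. Adding church-by-time brought the bias to about 0 and the rate to 4.1–5.7% in every scenario. The simulation error near 5% is √(0.05 × 0.95/1500) = 0.6 percentage points, so those rates are compatible with 5%.

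**The case against.** Several stronger readings are tempting, and the documents do not support them.

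- **A reader might infer that the adjusted models adjust nothing.** That is exact only for complete data. The plan allows for 30% attrition, and step 2 shows the main effects can then correct covariate-related missingness.
- **A reader might take it as documented that the covariates enter only as main effects.** The text is silent. Main effects are the natural reading, but it remains a reading.
- **A reader might infer that the moderator results are known to be contaminated.** This needs churches to differ both in paired-phase change and in moderator mix, and the documents report neither.
- **A reader might cite educators and curriculum adaptation as proof that churches differ while paired.** Those passages mainly concern the nine weekly classes. The dyad training and the reconvened group meeting were led by the PI (4.4.2.2). Church gaps that arise wholly before week 9 cause no bias in a week 9-to-18 contrast. If instead the before/after indicator is the time term, the mean of weeks 1 and 9 carries half of such a gap and the later mean all of it, so about half remains. The plan does not say which coding the interactions use.
- **A reader might want wider standard errors to reach beyond these churches.** The stated purpose is feasibility in three churches, so no such claim is made.

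It is also fair that participants could choose their own partner, that the same PI took part in matching at every site, and that 4.4.3 disclaims statistical significance as the aim. These points lower the severity. They do not supply the missing term: 4.6.3 still tests changes and moderators for significance.

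**Conclusion.** The point holds in a limited form. No church-by-time term is described, so church differences in change are not controlled in the three moderator tests, and those tests can be confounded by church. The plan makes this plausible: an educator is assigned to each church, lay leaders helped assign partners, and the plan's own Aim 1 analysis asks whether communication frequency differs by church. It does not show that confounding occurred.

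The size depends entirely on assumed church gaps and partner-choice shares. It runs from no bias when either is absent to about −0.5 kg with roughly 9–12% false positives in the moderate case (28 or 40 dyads), and more under strong imbalance. Agreement between unadjusted and adjusted change is weak evidence of robustness for weight-like outcomes. It is more informative where dropout is material and visits correlate less.

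This is a cheap improvement of minor severity. It concerns exploratory tests in a single-group pilot and leaves the feasibility aim untouched.

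**What to change.** In section 4.6.3:

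1. Write out the full model for each question, including the time coding and which covariates the moderator models carry.
2. Keep the covariate main effects, and keep the main effect of whichever moderator is being tested.
3. Add church-by-time, in the same time coding as the contrast tested, to each of the three moderator models and to the adjusted change model, at least as a sensitivity analysis.
4. Report the change in each church with a 95% CI, next to the pooled change for these three churches.

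No new data are needed. Three churches cost 3 − 1 = 2 degrees of freedom per time contrast. If visits are entered as categories, that is 2 × 3 = 6 for weight, BMI and systolic pressure (weeks 9, 14, 18 against week 1) and 2 × 2 = 4 for intake and activity (weeks 9 and 18). Intervals for the moderator terms will be slightly wider.

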4.4 Methods

4.4.1 Design Overview

This was a prospective multi-method 18-week feasibility study to explore using peer support dyads to augment an existing healthy weight promotion program, Faithful Families Thriving Communities (Faithful Families), in African American churches in North Carolina. The intervention included nine weeks of group health education classes, followed by nine weeks of dyads working together to achieve their health goals (Table 6). For the first nine weeks, participants attended weekly 90-minute group health education classes at their faith community. At the end of the nine weeks, each participant selected or was assigned a peer support partner. After attending one 90-minute dyadic training session, dyads worked together for the second nine weeks to improve fruit and vegetable consumption, physical activity, and other health goals they identified. The group reconvened twice during the second nine weeks to share progress. Before starting the program, all participants were consented in a private area of the church. The Duke University Institutional Review Board approved the study.

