4.5.3 Goal Attainment and Health Outcomes (Aim 2)

Weight, blood pressure, and BMI were measured at weeks 1, 9, 14, and 18 by the PI in a private area in the church. Blood pressure was taken using an Omron electronic cuff or Welch Allen manual blood pressure cuff if measures could not be obtained electronically, after participants were seated for three to five minutes. Systolic or diastolic pressures greater than 130 or 80 were considered high, 120-129 and 70-79 elevated, and less than 120 or 70 normal (American Heart Association, 2017a). Floor scales were used to measure weight. Height was self-reported for BMI calculations. BMI is a standard

measure of obesity based on an individual's weight in proportion to their height. Values greater than 29 kg/m² are considered obese, 25-29 kg/m² is overweight and 18.5-24.9 kg/m² is the normal range (American Heart Association, 2014).

Fruit and vegetable intake and physical activity were measured at weeks 1, 9, and 18 using survey items developed by the United States Department of Agriculture (USDA) Expanded Food and Nutrition Education Program (EFNEP) survey (Bradford, Serrano, Cox, & Lambur, 2010; National Institute of Food and Agriculture, 2018). Dietary intake is measured in two different ways. One is a 24 hour food recall which asks participants to write down all foods consumed in the past 24 hours, resulting in a summary of the number of vegetables and fruits eaten during that time period. The other question asks for the number of servings of fruits and of vegetables that participants think they eat each day, on average. These items are part of the entry and exit surveys normally completed by Faithful Families Thriving Communities participants and thus have been used successfully among African American churchgoers (Hardison-Moody et al., 2011). Cronbach's alpha of 0.6 at baseline, 0.7 at week nine, 0.6 at week 18, and 0.8 between all three time points showed acceptable internal consistency of the survey items used in this study. Finally, in semi structured interviews, participants were asked if any other social or environmental variables, such as access to food or places to exercise, influenced their ability to achieve their health goals.

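### Does the before/after-pairing indicator in section 4.6.3 credit half of the class-phase change to the peer-support phase?

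*Combined protocol and SAP*

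**What the plan says.** Section 4.6.3 of the combined protocol and SAP sets out three analyses of the health outcomes: change from baseline to week 18; a comparison of phases, in which "significant changes during the first nine weeks before participants were paired, compared to the second nine weeks after they were paired, were assessed"; and three separate models with interaction terms (relationship type, partner assignment, communication frequency) for change while participants were paired.

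The model is described thus: "A three-level mixed model (participants nested within dyads over time) was used to assess changes in weight, BMI", followed by the other outcomes. How time enters (linear, categorical or piecewise) is not stated, and Table 7 says only that a mixed model is used.

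The indicator appears in its own sentence, which opens with the reason for having it: "Dependence of participants during the second nine weeks was accounted for by". The device that the sentence then names is "creating a dichotomous variable to separate measurements taken before participants were paired and measurements taken after they were paired".

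On timing, section 4.4.1 says: "At the end of the nine weeks, each participant selected or was assigned a peer support partner". Section 4.5.3 gives two schedules: "Weight, blood pressure, and BMI were measured at weeks 1, 9, 14, and 18", and "Fruit and vegetable intake and physical activity were measured at weeks 1, 9, and 18".

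**The concern.** Week 9 closes the class phase and is also the starting point of the paired phase. An indicator that sorts measurements can put week 9 on one side only, and here that is before pairing. Used alone, it compares average levels before and after pairing, not the two changes that the plan sets out to compare. A gain made in the classes and merely held afterwards would then look like a gain after pairing, and a partial relapse could be masked.

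Diet and activity have only one visit after pairing, so an indicator-by-time interaction cannot give them a separate slope within the paired phase. The three planned interaction models would inherit whatever phase term is used.

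This matters because it is the plan's quantitative health-outcome comparison of the existing classes with the added peer support.

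**Working it through.** The plan states no figure for this contrast, so there is none to reproduce. The check asks what each plausible model estimates on the plan's own schedules.

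**Inputs.** Visits are weeks 1, 9, 18 (diet, activity) and weeks 1, 9, 14, 18 (weight, BMI, systolic pressure), from section 4.5.3. Week 9 is taken as measured before pairing, an assumption consistent with section 4.4.1. Let d1 be the change from week 1 to 9 and d2 the change from week 9 to 18, linear within each phase. Setting week 1 to 0, the means are d1 at week 9, d1 + (5/9)d2 at week 14 and d1 + d2 at week 18. Data are complete.

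**1. Indicator only, random intercept.** The coefficient is the mean after pairing minus the mean before.
- Three visits: (d1 + d2) − d1/2 = d2 + 0.5·d1.
- Four visits: d1 + (7/9)d2 − d1/2 = 0.5·d1 + 0.778·d2.

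For illustration, d1 = −2 and d2 = 0 gives −1.0 on both schedules. With d1 = −2 and d2 = +1 it gives 0.0 on three visits and −1 + 0.778 = −0.22 on four. Under this model the worry is real.

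The one-half is not general. With assumed first-order autoregressive correlation of 0.95 per week, the weight on d1 falls to 0.19 (three visits) and 0.12 (four). With an assumed random slope (variances 0.8 intercept, 0.002 slope, 0.2 residual) it is 0.11 and 0.19.

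**2. Indicator plus linear time, three visits.** Three means and three parameters, so the fit is saturated.
- Time coefficient: d1/8.
- Indicator coefficient: (d1 + d2) − 17·(d1/8) = d2 − (9/8)·d1 = 9 × (d2/9 − d1/8).
- Weekly slope in the paired phase: d1/8 + [d2 − (9/8)·d1]/9 = d2/9.

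The indicator coefficient is nine times the difference between the two weekly slopes, so testing it is the phase comparison. The paired-phase slope has standard error √2/9 = 0.1571 per unit residual SD, the same as piecewise time with a knot at week 9.

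**3. Indicator plus linear time, four visits, random intercept.** The coefficient is 0.533·d2 − 0.600·d1 = 4.8 × (d2/9 − d1/8). It is zero exactly when the weekly slopes agree. Over the covariances tried, the weight on d1 ran from −0.42 to −0.60, so class-phase change is not credited to pairing.

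**4. Indicator, time and their product.**
- Three visits: rank 3 for 4 parameters, so not estimable. The plan does not name this model.
- Four visits: rank 4 of 4, saturated. The week 9 to 18 change is recoverable, with per-week standard error √2/9 = 0.1571. Piecewise time gives 1/√40.67 = 0.1568, where 40.67 is the sum of squares of 0, 5 and 9 about their mean. The fitted slope between weeks 14 and 18 has standard error √2/4 = 0.354, but it estimates a different quantity, so comparing it with 0.157 does not measure lost precision.

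**5. Piecewise time, knot at week 9.** Full rank (3 of 3) on both schedules; it returns d1 and d2 exactly. Categorical visit also gives the week 9 to 18 change directly.

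**6. Interval length.** Weeks 1 to 9 span 8 weeks and weeks 9 to 18 span 9. A steady trend makes the raw second-phase change 9/8 = 1.125 times the first, a 12.5% difference that a per-week scale removes.

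**The case for a change.** The strongest opposing case is that the third set of analyses needs a term for change while paired, and the indicator is the only such term the plan names. Either the indicator is that term and mixes levels with changes, or the plan has no term at all. Depending on the reading, the weight on class-phase change runs from +0.5 to −1.125, so the same text could give coefficients of opposite sign on the same data. And although section 4.4.3 says that significance is not the aim, section 4.6.3 still assesses significant changes by phase.

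It stands that the coding and contrast are not written down, and that the indicator alone would be a poor choice. It does not stand that the readings are equally open. The plan states the quantity it wants, change against change, which a comparison of average levels does not deliver. The indicator has a stated purpose, partner dependence, and a model described as running over time to assess change points to a time term. The −1.125 is the trend comparison itself, expressed on a nine-week scale. For diet and activity, weeks 9 and 18 identify the paired-phase change, to which the interactions can attach.

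**Conclusion.** The concern does not call for a change. Crediting half of the class-phase change to pairing is exact only if the indicator is the sole time-related term, the covariance is a random intercept (with or without an added post-pairing effect), and data are complete. The plan fixes none of these conditions and gives the indicator another job. With linear time added, the class-phase change enters with a negative weight and the coefficient tests equality of weekly slopes. The week 9 to 18 change can be estimated on both schedules, and the coding costs essentially no precision (0.1571 against 0.1568 per week with four visits; equal with three).

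The gap is one of written detail. The target is clear, and a competent analyst would meet it with categorical visit or piecewise time anchored at week 9. The 8- versus 9-week interval is a matter of scale. Nor would more exact wording alter what the study can show: without a control group, no coding of phase separates peer support from elapsed time, and section 4.4.3 presents the quantitative outcomes as insight into patterns of change. These results assume change that is linear within each phase and a week 9 measurement taken before pairing; the effect of missing visits was not computed.
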